2.8.2 Laboratory data

2.8.2.1 CTC grading for laboratory parameters

Grade categorization of lab values will be assigned programmatically as per NCI Common Terminology Criteria for Adverse Events (CTCAE) version 4.03. The calculation of laboratory CTC grades will be based on the observed laboratory values only, clinical assessments will not be taken into account. The criteria to assign CTC grades are given in Novartis internal criteria for CTC grading of laboratory parameters. The latest available version of the document based on the underlying CTCAE version 4.03 at the time of analysis will be used.

For laboratory tests where grades are not defined by CTCAE v4.03, results will be graded by the low/normal/high (or other project-specific ranges, if more suitable) classifications based on laboratory normal ranges.

A severity grade of 0 will be assigned for all non-missing lab values not graded as 1 or higher. Grade 5 is not applicable. For laboratory tests that are graded for both low and high values, summaries will be done separately and labeled by direction, e.g., sodium will be summarized as sodium-low and sodium-high.

2.8.2.2 Imputation rules

CTC grading for blood differentials is based on absolute values.

If laboratory values are provided as '<X' (i.e. below limit of detection) or '>X', prior to conversion of laboratory values to SI unit, these numeric values are set to X.

The following rules will be applied to derive the WBC differential counts when only percentages are available for a xxx differential

$$\text{xxx count} = (\text{WBC count}) * (\text{xxx \%value} / 100)$$

Same rule will be applied for normal ranges.

Corrected calcium can be derived using the reported total calcium value and albumin at the same assessment using the following formula:

$$\text{Corrected Calcium (mg/dL)} = \text{Calcium (mg/dL)} - 0.8 [\text{Albumin (g/dL)} - 4]$$

In order to apply the above formula, albumin values in g/L will be converted to g/dL by multiplying by 0.1), calcium values in mmol/L will be converted to mg/dL by dividing by 0.2495. For calculation of laboratory CTC grades 0 and 1, the normal range for derived corrected calcium is set to the same limits (in mg/dL) as for calcium.

CTC grades for the derived absolute WBC differential counts (neutrophils, lymphocytes) and corrected calcium are as defined in the previous section.

For T4 when corresponding units are mcg/dL (microgram per deciliter) then it can be converted directly into ug/dL with no conversion factor applied (i.e. 1 mcg/dL = 1 ug/dL). For the units as pg/mL can be converted to ug/dL by dividing by 10000 (i.e. 1 pg/mL = 10⁻⁴ ug/dL)

For the laboratory parameters where the CTC grades depend on the normal ranges, when normal ranges are captured as 0 and 888888.xxx then the normal ranges and normal ranges indicator should not be present and the corresponding CTC grade should not be derived.

2.8.2.3 Data analysis

Laboratory data from all sources (central and local laboratories (as applicable)) will be combined. The summaries will include all assessments available for the lab parameter collected no later than 30 days after the last study treatment administration date (see [Section 2.8](#)).

The following listing will be produced for the laboratory data:

- Listing of all CTC grade 3 or 4 laboratory toxicities

The following by-treatment summaries will be generated separately for hematology and biochemistry tests:

- Worst post-baseline hematology and biochemistry based on CTC grades

For laboratory tests where grades are defined by CTCAE 4.03:

- Shift tables using CTCAE 4.03 grades to compare baseline to the worst on-treatment value

For laboratory tests where grades are not defined by CTCAE 4.03:

- Shift tables using the low/normal/high/ (low and high)

[Table 2-3](#) and [Table 2-4](#) list all laboratory parameters for which CTCAE grades are defined and for which CTCAE grades will be listed on local laboratory normal ranges respectively.

Table 2-3 Laboratory parameters for which CTCAE grades are defined

Hematology and coagulation		Biochemistry	
White Blood Cells (WBC)	↑↓	Creatinine	↑
Hemoglobin	↓	Sodium	↑↓
Platelets counts	↓	Potassium	↑↓
Absolute Neutrophils	↓	Corrected calcium	↑↓
Absolute Lymphocytes	↑↓	Magnesium	↑↓
		Albumin	↓
		AST (SGOT)	↑
		ALT (SGPT)	↑
		Total Bilirubin	↑
		Inorganic Phosphorus	↓
		amylase	↑
		lipase	↑
		Alkaline phosphatase	↑
		Fasting Glucose	↑↓

↑ Indicates that CTC grade increases as the parameter increases.

↓ Indicates that CTC grade increases as the parameter decreases.

Table 2-4 Laboratory parameters (without CTCAE grades) for which lab reference ranges are defined

Hematology and coagulation	Biochemistry
Hematocrit	Blood urea nitrogen (BUN)
Absolute Basophils	Urea*
Absolute Eosinophils	
	Direct Bilirubin
Absolute Monocytes	Indirect Bilirubin
	T4
	T4FR
	TSH
	Chloride
	Bicarbonate

*Urea will be converted to BUN and reported as BUN.

2.8.2.4 Hematology

Hematologic tests include: a complete blood count (CBC) consisting of a total white blood cell count (WBC) with differential (total neutrophil [including bands], lymphocyte, monocyte, eosinophil, and basophil counts), hematocrit, hemoglobin, and platelet count.

Differential counts will be converted to absolute values for CTC grade classification. For all the differential counts, percentages will be converted to absolute values, if necessary:

e.g. Absolute WBC diff (Wunit) = Absolute WBC (Wunit)*Relative WBCdiff(%)/100.

2.8.2.5 Biochemistry

Biochemistry includes the following parameters: urea or blood urea nitrogen (BUN), creatinine, sodium, potassium, corrected calcium, albumin, total bilirubin (also measure direct and indirect bilirubin if total bilirubin is > grade 1), alkaline phosphatase, AST (SGOT), ALT (SGPT), glucose, magnesium, chloride, bicarbonate, inorganic phosphorus (phosphate), amylase, and lipase.

2.8.2.6 Other clinical laboratory parameters

Coagulation includes the following parameters: Prothrombin time (PT) or international normalized ratio[INR], activated partial thromboplastin time (APTT).

Other parameters include thyroid function (total or free T4, TSH) and cytokines interleukin 6 (IL-6) [REDACTED].

2.8.3 Vital signs, weight and physical examinations

Vital sign assessments are performed in order to characterize basic body function. The following parameters are collected: systolic and diastolic blood pressure (mmHg), pulse rate (beats per minute), body temperature (°C), and weight (kg).

Vital signs collected during on-treatment period will be summarized. Values measured during the post-treatment period will be flagged in the listings. The number and percentage of patients with notable vital sign values (high/low) will be presented by treatment. For analysis of vital signs, the clinically notable vital sign criteria are provided in [Table 2-5](#).

Table 2-5 Criteria for notable vital sign values

Vital sign [unit]	Notable high value	Notable low value
Systolic blood pressure [mmHg]	≥180 mmHg with increase from baseline of ≥20 mmHg	≤90 mmHg with decrease from baseline of ≥20 mmHg
Diastolic blood pressure [mmHg]	≥105 mmHg with increase from baseline of ≥15 mmHg	≤50 mmHg with decrease from baseline of ≥15 mmHg
Pulse rate [bpm]	≥100 bpm with increase from baseline of >25%	≤50 bpm with decrease from baseline of >25%
Body temperature [°C]	≥ 39.1	--
Weight [kg]	≥10% increase from baseline	≥10% decrease from baseline

Vital signs shift table based on values classified as notable low, normal, notable high or notable (high and low) at baseline and worst post-baseline will be produced.

Descriptive statistics will be provided for baseline, for worst post-baseline value and change from baseline to worst post-baseline value for each vital sign measure.

Patients with any clinically notable vital sign value will be listed.

2.8.4 Electrocardiograms

2.8.4.1 ECG data descriptive statistics

The average of the ECG parameters at that assessment should be used in the analyses, if the average is associated with the nominal timepoint. If nominal timepoint is unavailable, the average will not be done and the individual values will be used. The following summaries will be provided for each applicable ECG parameter:

- Number (%) of patients having notable ECG values according to [Table 2-6](#).

Table 2-6 Criteria for notable ECG values

ECG parameter	Criteria for ECG notable values
QT, QTcF, QTcB (ms)	Increase from baseline >30 ms to ≤60 ms, >60 ms New QT/QTc >450 to ≤480ms; >480 to ≤500 ms; >500 ms
HR (bpm)	Increase from baseline >25% and value >100 bpm Decrease from baseline >25% and value <50 bpm
PR (ms)	Increase from baseline >25% and value >200 ms New PR >200 ms
QRS (ms)	Increase from baseline >25% and value >120 ms New QRS >120 ms

Patients with any notable change from baseline for each QT/QTc interval will be listed.

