### 1.2.3 Overview of the combination of LAG525 and PDR001

#### 1.2.3.1 Nonclinical experience with the combination of LAG525 and PDR001

Woo (Woo 2012) described a series of experiments with dual LAG-3/PD-1 knockout (KO) mice evaluating both tumor efficacy and the KO phenotype in these animals. Compared to wild-type (WT), the dual KO mice developed an early onset (4 weeks of age) of a lethal autoimmune condition that resulted in approximately 80% of the mice moribund by approximately 10 weeks. The major histopathologic manifestations included diffuse fibrosing lymphohistiocytic endocarditis, myocarditis, and pancreatitis. In contrast, LAG-3 and PD-1 single KO mice lacked any disease manifestations or histopathology over this period of observation. These results show that the PD-1 and LAG-3 pathways synergistically regulate immune self-reactivity. These results demonstrate a theoretical risk of the simultaneous disinhibition of both the LAG-3 and PD-1 receptor pathways. However, intermittent blocking of both receptors in patients where the pathways have been biologically and physiologically intact since birth seems unlikely to produce such a severe clinical picture. In addition, in the setting of a clinical trial with intense

safety monitoring and clear guidance on drug interruption and withdrawal, the management of immune adverse events should be possible. Any theoretical risk is also balanced by the well-documented efficacy of these agents, both alone and in combination, in a host of tumor models and for PD-1 inhibition in the clinical setting.

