**Table 7-5 12 Lead ECG collection plan**

Cycle	Day	Time
Screening	-21 to -1	Anytime
1	1	*Pre-dose
1	1	*1h (±5 min) hour post dose
2	1	*Pre-dose
2	1	*1h (±5 min) hour post dose
3	1	*Pre-dose
3	1	*1h (±5 min) hour post dose
4	1	*Pre-dose
4	1	*1h (±5 min) hour post dose
5	1	*Pre-dose
5	1	*1h (±5 min) hour post dose
6	1	*Pre-dose
6	1	*1h (±5 min) hour post dose
EoT	-	Anytime
Unscheduled**	-	Anytime

\*ECGs Performed in triplicate.  
\*\*A PK sample should be collected just after an ECG performed due to an unexpected cardiac signal.

All ECGs will be independently reviewed by a central laboratory. Instructions for the collection and transmission of ECGs to the central ECG laboratory will be provided in the ECG Manual.

After the primary CSR cut-off date is reached, ECGs will be performed at the discretion of the investigator and will be recorded on an unscheduled CRF page. These ECGs will not be reviewed by the central laboratory.

Clinically significant abnormalities present at screening should be reported on the Medical History CRF page. New or worsened clinically significant findings occurring after informed consent must be recorded on the Adverse Events CRF page. All eligibility and patient management decisions should be made based on the local reading of the ECG.

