### **10.5.3.4 Other safety data**

#### **ECG**

- shift table baseline to worst on-treatment result for overall assessments
- listing of ECG evaluations for all patients with at least one abnormality.

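### SAP 2.8.4.1 omits the two ECG outputs planned in Protocol 10.5.3.4, so qualitative ECG abnormalities that cross no numeric cut-off are tabulated only if reported as adverse events

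*SAP*

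**What the plan says.** Protocol 10.5.3.4 (Other safety data, ECG) lists two outputs:

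- "shift table baseline to worst on-treatment result for overall assessments"
- "listing of ECG evaluations for all patients with at least one abnormality"

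SAP 2.8.4.1 covers the same data. Its only summary is "Number (%) of patients having notable ECG values according to" Table 2-6. That table sets numeric criteria for QT, QTcF and QTcB, for heart rate (for example "Increase from baseline >25% and value >100 bpm"), and for PR and QRS. Its only ECG-specific listing is "Patients with any notable change from baseline for each QT/QTc interval will be listed".

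The SAP introduction says that this version rests on Protocol Amendment 10, which is the protocol version at hand. Both documents include ECG changes in the secondary safety endpoint (Protocol Table 3-1, SAP 1.2).

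**The concern.** An overall ECG assessment is the reader's judgement of the whole tracing. It is where rhythm disturbances and waveform changes are recorded. Table 2-6 works on interval lengths and heart rate, averaged over the tracings at a nominal time point. A tracing can be normal on all of these and still be abnormal overall.

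The protocol's shift table would show, by treatment group, how many patients moved from a normal to an abnormal ECG on treatment. Under the SAP text nobody is asked to produce that count. A secondary safety endpoint would then be reported from its numeric part alone. The qualitative part would enter a table only through a site's decision to report an adverse event.

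**Working it through.** No figure is stated on this point, so the check compares the texts.

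**1. Outputs side by side.**

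| Output | Protocol 10.5.3.4 | SAP 2.8.4.1 |
|---|---|---|
| Shift table of overall ECG assessment, baseline to worst on-treatment | Planned | Not named |
| Listing for patients with at least one ECG abnormality | Planned | Not named |
| Number (%) with notable numeric values | Not named | Planned (QT/QTc, heart rate, PR, QRS) |
| Listing of notable QT/QTc changes | Not named | Planned |

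Of the protocol's two outputs, 0 are carried into the SAP by name.

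**2. Is the choice left to the analysis plan?** For vital signs, Protocol 10.5.3.4 leaves the definition of notable results to the analysis plan. It has no such sentence for ECGs. The SAP keeps the vital-signs shift table in 2.8.3: "Vital signs shift table based on values classified as notable low, normal, notable high". The ECG shift table has no counterpart.

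**3. Can the same information come from elsewhere in the SAP?**

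- *Numeric table.* Table 2-6 counts some conduction changes, through PR and QRS, and heart-rate changes whatever the site thinks of them. It holds no qualitative category.
- *Adverse-event tables.* Protocol 7.2.2.6.1 requires new or worsened clinically significant ECG findings to be entered as adverse events, and SAP 2.8.1.2 tabulates on-treatment events. A finding not judged clinically significant does not take this route.
- *General listing.* SAP 2.8 says that safety assessments are listed. That may supply rows for each patient, but no count by treatment group.

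**4. What is left.** The residual gap is a qualitative abnormality that crosses no Table 2-6 cut-off and is not reported as an adverse event. Under the SAP text it appears in no table.

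**5. Are the data there?** The protocol schedules ECGs before and after dosing on Day 1 of Cycles 1 to 6, and states "All ECGs will be independently reviewed by a central laboratory". That review stops after the primary CSR cut-off, when ECGs become discretionary. No new data collection appears to be needed.

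**The case against.** The case for leaving the SAP alone has several sound parts.

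- *Clinically important findings are not lost.* They go to the adverse-event page and are tabulated, and events of special interest have their own summary in SAP 2.8.1.3. This stands. A reader might infer that rhythm and waveform findings go wholly unsummarised; the documents do not support that.
- *QT deserves the attention it gets.* QTcF is an exclusion criterion in Protocol 5.3, and QTc prolongation has its own entry in Protocol Table 6-5. A reader might also point to the dual-knockout mouse data in Protocol 1.2.3.1 ("The major histopathologic manifestations included diffuse fibrosing lymphohistiocytic endocarditis, myocarditis, and pancreatitis") and conclude that myocarditis, rather than QT, is the ECG risk the protocol names. It does not say so. It calls the risk theoretical, and although Grade 2 myocarditis is a dose-limiting toxicity in Table 6-4, no passage ties the scheduled ECGs to detecting it. The QT outputs are legitimate; the point is that they are not sufficient.
- *The listing is largely covered.* The general statement in SAP 2.8 would include ECGs if taken literally. This softens the loss of the abnormal-ECG listing. It does nothing for the shift table.
- *Nothing shows a silent deletion.* The SAP change history records changes between SAP versions. No earlier SAP is available to show that these outputs were ever in it. What is shown is an unexplained difference between protocol and SAP, and no more.
- *The output shells are a separate document.* They were not available and may contain the table. If they do, the SAP text should call for it.

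After all of this the omission remains. No adverse-event table or raw listing replaces a by-treatment count of the overall ECG assessment.

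**Conclusion.** The point holds as a protocol–SAP mismatch on a descriptive secondary safety output. Neither of the protocol's two ECG outputs is named in SAP 2.8.4.1, no reason is given, and the numeric counts and QT/QTc listing do not replace them. The practical loss is confined to qualitative abnormalities below every Table 2-6 cut-off that were not reported as adverse events.

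How many patients that concerns cannot be derived, because the documents give no event rate. Counting scheduled tracings would measure the collection effort, not the number of findings missed, so no size is attached on that basis.

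The conclusion rests on two assumptions: that the SAP text, rather than the unseen shells, governs which outputs are produced; and that the database holds an overall ECG assessment, as the protocol's shift table presupposes. The primary analyses are not affected. The change is still worth making: the output was planned, it belongs to a stated endpoint, and it is cheap to restore.

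**What to change.** In SAP 2.8.4.1, by treatment group (disease group in Phase II), add:

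1. a shift table of the overall ECG assessment from baseline to worst on-treatment result;
2. a listing of ECG evaluations for every patient with at least one abnormality.

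State whether the overall assessment comes from the local or the central reading, since Protocol 10.5.3.4 does not specify this. If the outputs are left out on purpose, record the departure from the protocol and the reason.

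Extending the notable-value listing to PR, QRS and heart rate is optional once the abnormal-ECG listing is back.

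The cost is one table, one listing and a few lines of SAP text, from data the protocol already collects. No visit, procedure or treatment rule changes.

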2.8.5 Tolerability

Tolerability of study treatment will be assessed by summarizing the number of dose interruptions and dose reductions by treatment group. Reasons for dose interruption and dose reductions will be listed by patient and treatment group and summarized by treatment group. Relative dose intensity of study treatment (see [Section 2.5.1](#)) will be also be used to assess tolerability.

Biofluid concentrations will be expressed in mass per volume units. All concentrations below the limit of quantitation or missing data will be reported as such in the concentration data listings. Concentrations below the limit of quantitation will be treated as zero in summary statistics.

Descriptive statistics of all pharmacokinetic parameters will include arithmetic and geometric mean, median, SD, and CV, geometric CV, minimum and maximum. Zero concentrations will not be included in the geometric mean calculation. Since T_{max} is generally evaluated by a nonparametric method, median values and ranges will be given for this parameter.

Summary statistics will be presented for LAG525 serum concentrations at each scheduled time point. Descriptive graphical plots of individual serum concentration versus time profiles and mean concentration versus time profiles will be generated.

Missing concentration values will be reported as is in data listings. Concentration values below Lower limit of quantitation (LLOQ) will be handled as zero in summary statistics, and reported as is in data listings. Any missing pharmacokinetic parameter data will not be imputed.

Further analyses may be conducted using population PK approaches.

Dose proportionality

The analysis of dose proportionality will be conducted for AUC and C_{max} of single agent LAG525, LAG525 in combination with PDR001 and PDR001 in combination with LAG525 using a power model on log-transformed scale. The log-transformed PK parameters will each be regressed onto a fixed factor for log (dose). The 90% confidence interval (CI) of the slope for each PK parameter will be computed from the model and presented in a summary table. For LAG525 as a single agent and for LAG525 when in combination with PDR001 dose proportionality will be assessed for C_{max} and AUC(0-336h) for Q2W regimen, and for C_{max} and AUC(0-672h) for Q4W regimen respectively, only for Cycle 1 and 3 separately within the same output, considering every dose level except flat doses, when single agent, and flat dose levels only when in combination. For LAG525 when in combination with PDR001, for Q3W regimen, dose proportionality will be assessed for C_{max} and AUC(0-504h) for Cycles 1 and 3 separately within the same output. For PDR001 when in combination with LAG525 dose

proportionality will be assessed for Cmax and AUC(0-336h) for Q2W, and for Cmax and AUC(0-672h) for Q4W, for Cycles 1 and 3 separately within the same output, considering flat dose levels only.

2.10 Biomarkers

[Redacted]

[Redacted]

[Redacted]

Table 2-8 Biomarkers and purpose of analysis

Biomarker	Purpose of analysis
[Redacted]	[Redacted]
[Redacted]	[Redacted]
[Redacted]	[Redacted]

Biomarker	Purpose of analysis
Anti-LAG525/ anti-PDR001 antibodies	Assess emergence of anti-LAG525/anti-PDR001 antibodies following one or more intravenous (i.v.) infusions of LAG525/PDR001

Please see the next section for details on the analysis of emergence of anti-drug antibodies.

2.11 PD and PK/PD analysis

2.11.1 Immunogenicity

2.11.1.1 Sample ADA Status

Each IG sample is assessed in a three tiered anti-drug anti-body (ADA) testing approach. All IG samples are analyzed in the initial screening assay (first tier). Samples testing negative in the screening assay are not subject to a confirmatory assay. Samples testing positive in the screening assay are then subjected to the confirmatory assay to demonstrate that ADA are specific for the therapeutic protein product (second tier). The titer of confirmatory positive samples will be subsequently determined in the titration assay (third tier). Samples identified as positive in the confirmatory assay are considered ADA positive. Samples can test negative in either the screening or confirmatory assay but for analysis purposes they are not differentiated. The following properties of each sample will be provided in the source data:

- Result of assay according to pre-specified confirmatory cut point: ADA positive (yes) or ADA negative (no)
- Titer (for positive samples): numerical representation of the magnitude of ADA response
- Drug tolerance level: highest drug concentration that does not interfere in the ADA detection method
- Fold titer change (i.e. x-fold): threshold for determining treatment boosted

Determinant samples are defined as samples which are not unevaluable (where unevaluable = sample where assay is not available).

The following definitions apply only to determinant samples:

- ADA-negative sample: Determinant sample where assay is ADA negative and LAG525 (PDR001) PK concentration at the time of IG sample collection is less than the drug tolerance level.

- ADA-positive sample: Determinant sample where assay is ADA positive.
- ADA-inconclusive sample: Sample where assay is ADA negative and LAG525 (PDR001) PK concentration at the time of IG sample collection is greater than or equal to the drug tolerance level or missing.

The following definitions apply only to post-baseline ADA-positive samples with a corresponding determinant baseline sample. To be classified as treatment-boosted or treatment-unaffected, both the post-baseline and baseline titer must be non-missing:

- treatment-induced ADA-positive sample: ADA-positive sample post-baseline with ADA-negative sample at baseline.
- treatment-boosted ADA-positive sample: ADA-positive sample post-baseline with titer that is at least the fold titer change greater than the ADA-positive baseline titer.
- treatment-unaffected ADA-positive sample: ADA-positive sample post-baseline with titer that is less than the fold titer change greater than the ADA-positive baseline titer.

NOTE: PK concentrations which are flagged for exclusion will still be used to determine ADA-inconclusive and ADA-negative samples.

The following summaries of ADA sample status (n and %) will be provided using Immunogenicity prevalence set:

- ADA-positive samples (i.e. ADA prevalence), overall and by time point (including baseline). For summaries by time point, the denominator is the number of patients at that time point with a determinant sample.

Listings will be provided of sample ADA status (including titer for positive samples).

